#### 6.10.1 Definition of Measurable/Non-Measurable and Index/Non-Index Lesions

Definitions of lesions are based on *mWHO criteria or immune-related response criteria (irRC)* in this study.

##### ***Definition of Measurable and Non-Measurable Lesions***

**Measurable Lesions** are lesions that can be accurately measured in two perpendicular diameters, with at least one diameter  $\geq 20$  mm and the other dimension  $\geq 10$  mm (10 mm x 10 mm for spiral CT). The area will be defined as the product of the largest diameter with its perpendicular. Skin lesions can be considered measurable.

**Non-Measurable (evaluable) Lesions** are all other lesions, including unidimensionally measurable disease and small lesions (lesions without at least one diameter  $\geq 20$  mm), and any of the following:

- Lesions occurring in a previously irradiated area (unless they are documented as new lesions since the completion of radiation therapy), bone lesions, leptomeningeal disease, ascites, pleural or pericardial effusion, lymphangitis cutis/pulmonis, abdominal masses that are not pathologically/cytologically confirmed and followed by imaging techniques and cystic lesions.
- All measurable and non-measurable lesions should be measured at screening and at the defined tumor assessment timepoints (see Section 5, Table 2). Extra

assessments may be performed, as clinically indicated, if there is a suspicion of progression.

### ***Definition of Index/Non-Index Lesions***

All measurable lesions, up to a maximum of **five lesions per organ** and **ten lesions in total**, should be identified as *index* lesions to be measured and recorded on the medical record at Screening. The *index* lesions should be representative of all involved organs. In addition, *index* lesions should be selected based on their size (lesions with the longest diameters), their suitability for accurate repeat assessment by imaging techniques, and how representative they are of the patient's tumor burden. At Screening, a sum of the products of diameters (SPD) for all *index* lesions will be calculated and considered the baseline sum of the products of diameters. Response criteria to be followed are listed below. The baseline sum will be used as the reference point to determine the objective tumor response of the *index* lesions at tumor assessment (TA).

Measurable lesions, other than *index* lesions, and all sites of non-measurable disease, will be identified as *non-index* lesions. *Non-index* lesions will be recorded on the medical record and should be evaluated at the same assessment time points as the *index* lesions. In subsequent assessments, *non-index* lesions will be recorded as "stable or decreased disease," "absent," or "progression."

### **6.10.2 Modified World Health Organization criteria for response**

The mWHO criteria were developed as a hybrid tumor response classification system using elements of both the WHO and RECIST criteria in an attempt to more accurately measure tumor lesions and estimate tumor responses.

### ***Definition of Index Lesion Response Using mWHO Criteria***

**Complete Response:** Complete disappearance of all *index* lesions.

**Partial Response:** Decrease, relative to baseline, of 50% or greater in the sum of the products of the two largest perpendicular diameters of all *index* lesions.

**Stable Disease:** Does not meet criteria for complete or partial response, in the absence of progressive disease. Subject with PR or CR that is not confirmed after at least 4 weeks are scored as SD unless they have new primary lesions.

**Progressive Disease:** At least 25% increase in the sum of the products of all *index* lesions (taking as reference the smallest sum recorded at or following baseline) and/or the appearance of **any** new lesion(s).

### ***Definition of Non-Index Lesion Response Using mWHO***

**Complete Response:** Complete disappearance of all *non-index* lesions.

**Stable Disease:** A decrease or tumor stabilization of one or more *non-index* lesions. Subject with PR or CR that is not confirmed after at least 4 weeks are scored as SD unless they have new primary lesions.

**Progressive Disease:** Progression of *non-index* lesion(s) (e.g., an increase in pleural effusions, or other fluid collections defined as an approximate doubling of the volume which was present at baseline or nadir, unless there is radiographic evidence of a benign cause for the fluid collection or the effusion is cytologically negative for malignant cells).

**Determination of Overall Response Using mWHO**

Overall Response (OR) is determined as the combination of assessments of *index* and *non-index* lesions using the following criteria:

Index Assessment	Lesion	Non-Index Lesion Assessment	New Lesions	Overall Response
CR		CR	No	CR
CR		SD	No	PR
PR		CR or SD	No	PR
SD		CR or SD	No	SD
PD		Any	Yes or No	PD
Any		PD	Yes or No	PD
Any		Any	Yes	PD

Best OR is the best confirmed response designation over the study as a whole, recorded between the date of first dose until the last tumor assessment for the individual patient in the study. The assessment of response at 12 weeks has particular emphasis due to the mechanism of action of ipilimumab inducing immune responses as basis for clinical responses. For the assessment of best OR, all available assessments per patient are considered. CR or PR determinations included in the best OR assessment must be confirmed by a second (confirmatory) evaluation meeting the criteria for response and performed no less than 4 weeks after the criteria for response are first met.

Patients will be assessed for efficacy by CT of chest, abdomen, and pelvis at baseline and every 6 weeks while on study and every 3 months thereafter, regardless of the location of known metastases. Similar methods of tumor assessment and similar techniques must be used to characterize each identified and reported lesion at screening and during subsequent tumor assessments. Imaging-based evaluation is preferred to clinical examination.

MRI of the brain will be used if brain metastases are being treated on study or if neurologic symptoms suggest concern for new or progressive disease within the brain.

If progressive disease is assessed based only on a new lesion(s) found on bone scans, additional imaging studies of the lesion(s) should be performed to confirm the malignant nature of the new findings on the bone scan. Increased intensity of uptake in previously abnormal areas on bone scans is not considered progressive disease, unless

the lesions seen on the correlative imaging studies performed of this area meet the criteria for progression. New areas of abnormal uptake on a bone scan represent progressive disease.

### 6.10.3 Definition of Tumor Response Using irRC

The sum of the products of diameters at tumor assessment using the irRC for progressive disease incorporates the contribution of new measurable lesions. Each net Percentage Change in Tumor Burden per assessment using irRC criteria accounts for the size and growth kinetics of both old and new lesions as they appear.

#### ***Definition of Index Lesions Response Using irRC***

**irComplete Response (irCR):** Complete disappearance of all *index* lesions. This category encompasses exactly the same subjects as “CR” by the mWHO criteria.

**irPartial Response (irPR):** Decrease, relative to baseline, of 50% or greater in the sum of the products of the two largest perpendicular diameters of all *index* and all new measurable lesions (i.e., Percentage Change in Total Tumor Burden). Note: the appearance of new measurable lesions is factored into the overall tumor burden, but does not automatically qualify as progressive disease until the SPD increases by  $\geq 25\%$  when compared to SPD at nadir.

**irStable Disease (irSD):** Does not meet criteria for irCR or irPR, in the absence of progressive disease.

**irProgressive Disease (irPD):** At least 25% increase Percentage Change in Tumor Burden (i.e., taking sum of the products of all *index* lesions and any new lesions) when compared to SPD at nadir.

#### ***Definition of Non-Index Lesions Response Using irRC***

**irComplete Response (irCR):** Complete disappearance of all *non-index* lesions. This category encompasses exactly the same subjects as “CR” by the mWHO criteria.

**irPartial Response (irPR) or irStable Disease (irSD):** *non-index* lesion(s) are not considered in the definition of PR, these terms do not apply.

**irProgressive Disease (irPD):** Increases in number or size of *non-index* lesion(s) does not constitute progressive disease unless/until the Percentage Change in Tumor Burden increases by 25% (i.e., the SPD at nadir of the index lesions increases by the required amount).

#### ***Impact of New Lesions on irRC***

New lesions in and by themselves do not qualify as progressive disease. However their contribution to total tumor burden is included in the SPD which in turn feeds into the irRC criteria for tumor response. Therefore, new non-measurable lesions will not discontinue any subject from the study.

**Definition of Overall Response Using irRC**

Overall response using irRC will be based on these criteria: The sum of the products of the two largest perpendicular diameters of all index lesions is measured and captured as the SPD baseline. At each subsequent tumor assessment, the sum of the products of the two largest perpendicular diameters of all index lesions and of new measurable lesions are added together to provide the Immune Response Sum of Product Diameters (irSPD).

**Immune-Related Complete Response (irCR):** Complete disappearance of *all* tumor lesions (index and nonindex together with no new measurable/unmeasurable lesions) for at least 4 weeks from the date of documentation of complete response.

**Immune-Related Partial Response (irPR):** A decrease, relative to baseline of the irSPD compared to the previous SPD baseline, of 50% or greater is considered an immune Partial Response (irPR).

**Immune-Related Stable Disease (irSD):** irSD is defined as the failure to meet criteria for immune complete response or immune partial response, in the absence of progressive disease.

**Immune-Related Progressive Disease (irPD):** It is recommended in difficult cases to confirm PD by serial imaging. Any of the following will constitute progressive disease:

- At least 25% increase in the sum of the products of all index lesions over baseline SPD calculated for the index lesions.
- At least a 25% increase in the sum of the products of all index lesions and new measurable lesions (irSPD) over the baseline SPD calculated for the index lesions.

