#### **Permanent Discontinuation of Ipilimumab**

##### ***Permanent Discontinuation for Related Adverse Events***

Permanently discontinue ipilimumab for any of the following:

Persistent moderate adverse reactions or inability to reduce corticosteroid dose to 7.5 mg prednisone or equivalent per day.

Severe or life-threatening adverse reactions, including any of the following:

- Colitis with abdominal pain, fever, ileus, or peritoneal signs; increase in stool frequency (7 or more over baseline), stool incontinence, need for

intravenous hydration for more than 24 hours, gastrointestinal hemorrhage, and gastrointestinal perforation

- Aspartate aminotransferase (AST) or alanine aminotransferase (ALT) >5 times the upper limit of normal or total bilirubin >3 times the upper limit of normal
- Stevens-Johnson syndrome, toxic epidermal necrolysis, or rash complicated by full thickness dermal ulceration, or necrotic, bullous, or hemorrhagic manifestations
- Severe motor or sensory neuropathy, Guillain-Barré syndrome, or myasthenia gravis
- Severe immune-mediated reactions involving any organ system (eg, nephritis, pneumonitis, pancreatitis, non-infectious myocarditis, hypophysitis)
- Immune-mediated ocular disease that is unresponsive to topical immunosuppressive therapy
- Any adverse event, laboratory abnormality or intercurrent illness which, in the judgment of the investigator, presents a substantial clinical risk to the patient with continued dosing.
- The development of progression as defined in the irRC as at least a 25% increase in tumor burden compared with nadir (at any single time point) in 2 consecutive observations at least 4 weeks apart and/or clinical deterioration of

subject's condition such that further benefit from ipilimumab dosing is unlikely or requires a change of therapy at the treating physician's discretion.

Please refer to the IB for specific treatment algorithms.

**The following neurological adverse event requires permanent discontinuation of ipilimumab and defines unacceptable neurotoxicity:**

- Any motor neurologic toxicity  $\geq$  Grade 3 regardless of causality
- Any  $\geq$  Grade 3 treatment related sensory neurologic toxicity

Please refer to the IB for specific treatment algorithms.

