**Table 11: Immune-Related Response Criteria Definitions**

Index Lesion Definition	Non-Index Lesion Definition	New Measurable Lesions	New Unmeasurable Lesions	Percent change in tumor burden (including new lesions when present)	Overall irRC Response
Complete Response	Complete Response	No	No	-100%	irCR
Partial Response	Any	Any	Any	≥ -50% <-50% <+25%	irPR to irSD

Index Lesion Definition	Non-Index Lesion Definition	New Measurable Lesions	New Unmeasurable Lesions	Percent change in tumor burden (including measurable new lesions when present)	Overall irRC Response
Stable Disease	Any	Any	Any	>+25% <-50% <+25%	irPD to irSD
Progressive Disease	Any	Any	Any	>+25% ≥+25%	irPD irPD

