Appendix III: Comparison between WHO criteria and the irRC

	WHO	irRC
New, measurable lesions (i.e., $\geq 5 \times 5$ mm)	Always represent PD	Incorporated into tumor burden
New, nonmeasurable lesions (i.e., $< 5 \times 5$ mm)	Always represent PD	Do not define progression (but preclude irCR)
Non-index lesions	Changes contribute to defining BOR of CR, PR, SD, and PD	Contribute to defining irCR (complete disappearance required)
CR	Disappearance of all lesions in two consecutive observations not less than 4 wk apart	Disappearance of all lesions in two consecutive observations not less than 4 wk apart
PR	$\geq 50\%$ decrease in SPD of all index lesions compared with baseline in two observations at least 4 wk apart, in absence of new lesions or unequivocal progression of non-index lesions	$\geq 50\%$ decrease in tumor burden compared with baseline in two observations at least 4 wk apart
SD	50% decrease in SPD compared with baseline cannot be established nor 25% increase compared with nadir, in absence of new lesions or unequivocal progression of non-index lesions	50% decrease in tumor burden compared with baseline cannot be established nor 25% increase compared with nadir
PD	At least 25% increase in SPD compared with nadir and/or unequivocal progression of non-index lesions and/or appearance of new lesions (at any single time point)	At least 25% increase in tumor burden compared with nadir (at any single time point) in two consecutive observations at least 4 wk apart

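### Overall irRC progression is measured from baseline in the overall-response definition but from nadir elsewhere in the protocol, which can delay irPD and raise irRC PFS

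*Combined protocol and SAP*

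**What the plan says.** Section 6.10.3 gives three sets of irRC definitions and a summary table.

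- **Overall response.** The text opens by saying that overall irRC response rests on the criteria listed there. Either of two findings is irPD: "At least 25% increase in the sum of the products of all index lesions over baseline SPD calculated for the index lesions", or the same percentage rise in the sum for index lesions "and new measurable lesions (irSPD) over the baseline SPD calculated for the index lesions".
- **Index lesions.** irPD is a 25% rise in the summed products of index lesions and "any new lesions) when compared to SPD at nadir".
- **Non-index lesions.** Growth does not count until the burden rises by 25%, explained as the point where "the SPD at nadir of the index lesions increases by the required amount".
- **Table 11.** The +25% and -50% cut-offs share a column headed "Percent change in tumor burden (including measurable new lesions when present", with no reference point named.

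Two other places define irRC progression. The permanent-discontinuation list in Section 5.4 uses "at least a 25% increase in tumor burden compared with nadir (at any single time point) in 2 consecutive observations". Appendix III, in its irRC column, uses "At least 25% increase in tumor burden compared with nadir (at any single time point) in two consecutive observations at least 4 wk apart".

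For comparison, mWHO progression in Section 6.10.2 is a 25% rise "taking as reference the smallest sum recorded at or following baseline".

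Six-month PFS by irRC is a secondary objective (Section 2.2), and PFS to first irRC progression is a secondary endpoint (Section 3.3). Neither names a reference point.

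**The concern.** Baseline and nadir are the same reference only while a patient's tumor burden has never fallen below baseline. Once it has, a rule tied to baseline lets the tumor regrow through all the lost volume, and a further 25% beyond it, before irPD is called. This regimen is meant to produce that shrinkage: SABR is given to one to three sites between the second and third ipilimumab doses. Irradiated index lesions may shrink while new lesions appear elsewhere, and the second overall trigger covers that case.

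The irRC PFS rate and the irRC progression date are at stake. The endpoint could also record no progression on scans that meet the irRC tumor-burden threshold in the stopping rule. Section 3.1.2 keeps patients on study until progression by both criteria or death, so time on study could change as well.

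**Working it through.** **The plan's own figure.** Section 7.1 tests a 6-month rate of 15% against 35% with both error rates held to 10%, and declares promise at 8 or more of 32. The exact binomial calculation for that rule gives a type I error of 0.0958 and power of 0.918, so N = 32 reproduces. It rests on mWHO progression, which already uses the smallest sum, so nothing below alters it.

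**Inputs.** Let baseline SPD = 1 and let s be the fractional shrinkage at nadir, so the nadir SPD is 1 - s. The 25% threshold is common to all the definitions. I take nadir as the smallest sum at or after baseline, as the mWHO text does, because the irRC text does not define the word.

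**Formulas.**

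1. Total SPD at which irPD is reached: 1.25 under the baseline rule, 1.25(1 - s) under the nadir rule.
2. Regrowth from nadir needed under the baseline rule: 1.25/(1 - s) - 1. Under the nadir rule it is always 25%.
3. New measurable disease needed if index lesions stay at nadir: 1.25 - (1 - s) = 0.25 + s under the baseline rule, 0.25(1 - s) under the nadir rule.

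**Results.**

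| Shrinkage at nadir | Regrowth needed, baseline rule | Total SPD (% of baseline) where only the nadir rule calls irPD | New-lesion SPD needed, baseline rule (% of baseline) | New-lesion SPD needed, nadir rule (% of baseline) |
|---|---|---|---|---|
| 25% | 1.25/0.75 - 1 = 67% | 93.75 up to 125 | 50 | 18.75 |
| 50% | 1.25/0.50 - 1 = 150% | 62.5 up to 125 | 75 | 12.5 |
| 75% | 1.25/0.25 - 1 = 400% | 31.25 up to 125 | 100 | 6.25 |

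With s = 0 both rules give 25% and agree.

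**Example.** SPD of 10, then 4, then 12 cm². From nadir, 12/4 - 1 = +200%, which meets the irPD threshold. From baseline, 12/10 - 1 = +20%, which is irSD.

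**Direction.** Nadir never exceeds baseline, so any scan that reaches 1.25 times baseline also reaches 1.25 times nadir. If the same confirmation rule is applied to both, the baseline rule can only give the same or a later irPD date, and the same or a higher irRC PFS.

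**Effect on the rate.** With 32 evaluable patients, one patient classified differently at 6 months moves the rate by 1/32 = 3.1 points. The documents do not say how many patients shrink and then regrow within the window, so the total effect cannot be computed.

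**The case against.** The strongest reply is that the overall-response text governs the endpoint. It says overall response rests on its own criteria, while the nadir texts are lesion-level definitions, a drug-stopping rule and a comparison table. That is a fair reading, and it means the plan is not simply silent on which text to apply. But it makes baseline the rule most naturally applied to irRC PFS, which is the problem. The opening sentence does not address the nadir definitions or give a reason for departing from them.

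Several limits stand. irRC PFS is secondary and carries no hypothesis or decision threshold. Section 6.10 also accepts clinical and biopsy evidence of progression, which may capture some cases sooner. Section 1.5.3 reports that most objective responders stay free of progression for long periods, so the effect at 6 months may be small. The clash with the stopping rule rarely arises during induction: scans are scheduled before the third infusion and at about week 14, while the last induction dose is at week 10. It matters mainly for optional re-induction.

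Three stronger readings are tempting, and the documents do not support them.

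- **Table 11 settles the matter for nadir.** A reader might infer this if the table's first column uses the index-lesion categories defined earlier in Section 6.10.3. Those categories already count new lesions, so a row leading from stable index disease to irPD on total burden could not occur. The table is also damaged in the available text.
- **The plan's irRC PFS is too high on balance.** Confirmation works the other way. The stopping rule and Appendix III require two assessments at least four weeks apart, the overall definition only advises serial imaging for hard cases, and Section 1.6 leaves confirmation to the investigator. With SPD of 10, 13, then 9, the overall definition allows irPD at the second scan (+30%), while a two-assessment rule does not. Section 1.5.3 describes such early rises with ipilimumab, so the net direction is unknown.
- **The primary endpoint is affected.** One line in Section 6.10 mentions PFS by both criteria together, but Section 3.2 ties the primary endpoint to mWHO alone.

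**Conclusion.** The point holds as an error in the written definition and should be fixed. Both overall irPD triggers use baseline where every other irRC progression definition that names a reference uses nadir. The regrowth required from nadir rises from 25% to 67%, 150% or 400% after shrinkage of 25%, 50% or 75%. The upward direction of the effect on irRC PFS assumes that nadir includes baseline, that confirmation is handled identically under both rules, and that progression is called by measurement. Confidence is high for the textual conflict and the thresholds. The size of the effect on the reported irRC PFS remains unknown.

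**What to change.** 1. In both irPD triggers of the overall irRC definition, replace the baseline SPD with the nadir SPD or irSPD, defined as the smallest sum at or after baseline.
2. In Table 11, label the +25% threshold as measured from nadir and the -50% threshold as measured from baseline.
3. State that this definition governs irRC PFS.
4. State how relapse is called after irCR, where nadir is 0 and a percentage rise is undefined. The rule should respect the section on new lesions, under which they are not progression by themselves.

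These are text edits that need no extra patients or scans. The price is that irRC PFS may come out somewhat shorter for patients who shrink and regrow.

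The mismatch on confirmation should be put to the sponsor separately. Mandatory confirmation is not part of this fix: it can lengthen irRC PFS, it would override the discretion in Section 1.6, and a rise first seen at the 6-month scan would remain unconfirmed until a later scan, which Appendix II leaves to the treating physician.
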